3. STUDY DESIGN

[figure not shown]
INCB 18424-306 and -307 are randomized, vehicle-controlled studies in adolescent and adult participants (age \geq 12 years) with nonsegmental vitiligo who have depigmented area including \geq 0.5% BSA on the face, \geq 0.5 F-VASI, \geq 3% BSA on nonfacial areas, \geq 3 T-VASI, and for whom total body involved vitiligo area (facial and nonfacial) does not exceed 10% BSA. Approximately 300 participants will be randomized 2:1 to receive initial study treatment (ruxolitinib cream 1.5% BID:vehicle) for 24 weeks. Participants will be stratified by region (North America or Europe) and skin type (Fitzpatrick scale Type I and II vs Type III, IV, V, and VI). Adolescents (\geq 12 to $<$ 18 years) will make up at least 10% of the study population, and no more than 50% of participants will be $>$ 40 years old.

After completion of the Week 24 assessments, participants will be offered the opportunity to receive an additional 28 weeks of treatment extension with ruxolitinib cream 1.5% BID. To be eligible for the treatment extension, participants must have completed the baseline and Week 24 visit assessments, be compliant with study procedures, and not have any safety issues. The total treated area should not exceed 10% BSA (facial and nonfacial).

Participants who successfully complete the 52-week treatment in this study may be eligible to participate in a separate extension study to evaluate durability of effect and maintenance regimens.

The study schema is shown below in [Figure 1](#). All participants will have follow-up assessments 30 (+ 7) days after the last application of study drug.

Figure 1: Study Design Schema

3.1. Randomization

Approximately 300 participants will be randomized 2:1 to receive initial study treatment (ruxolitinib cream 1.5% BID:vehicle) for 24 weeks. Participants will be stratified by skin type (Fitzpatrick scale Type I and II vs Type III, IV, V, and VI) and region (North America or Europe).

3.2. Control of Type I Error

The gatekeeping testing strategy for the primary and key secondary analyses will be implemented to control the overall Type I error rate, 2-sided $\alpha = 0.05$. These endpoints will be tested in a fixed sequence at 2-sided $\alpha = 0.05$ level in the following order:

- Proportion of participants achieving F-VASI75 at Week 24
- Proportion of participants achieving F-VASI50 at Week 24
- Proportion of participants achieving F-VASI90 at Week 24
- Proportion of participants achieving T-VASI50 at Week 24
- Vitiligo – VNS Response at Week 24
- Percentage change from baseline in F-BSA at Week 24

The endpoint will be tested only if the primary endpoint (and the secondary endpoints in previous steps) are rejected.

3.3. Sample Size Considerations

Approximately 300 participants will be randomized 2:1 to ruxolitinib cream 1.5% BID or vehicle and stratified by baseline skin type (Fitzpatrick scale Type I and II vs Type III, IV, V, and VI) and region (North America or Europe). The sample size is calculated to provide sufficient power ($> 85\%$) to detect a difference between the 1.5% BID with the vehicle in primary and key secondary endpoints. The powers for different endpoints are provided in [Table 2](#). The Fisher's exact test with a 2-sided alpha of 0.05 is used to provide a conservative evaluation of statistical power, and it is accurate when there is a small expected number of responders in the vehicle group.

Table 2: Powering for Primary and Key Secondary Endpoints

Endpoints	Response Rates in Ruxolitinib 1.5% BID ^a	Response Rates in Vehicle ^a	Power ^b
F-VASI75 at Week 24	20%	5%	95%
F-VASI50 at Week 24	30%	10%	95%
F-VASI90 at Week 24	10%	1%	88%
T-VASI50 at Week 24	10%	1%	88%
Vitiligo - VNS Response at Week 24	10%	1%	88%

^a Based on the results from a Phase 2, randomized, dose-ranging study (INCB18424-211).

^b Based on the Fisher's exact test with a 2-sided alpha of 0.05.

3.4. Schedule of Assessments

Refer to Protocol Amendment 3-US-CA dated 13 MAR 2020 for a full description of all study procedures and assessment schedules (Protocol Tables 3 and 4) for this study.

4. DATA HANDLING DEFINITIONS AND CONVENTIONS

4.1. Scheduled Study Evaluations and Study Periods

4.1.1. Day 1

Day 1 is the date that the first application of ruxolitinib cream or vehicle cream is administered to the participants in the specific period.

For randomized participants not treated with any study drug, Day 1 is defined as the day of randomization.

4.1.2. Study Day

If a visit/reporting date is on or after Day 1, then the study day at the visit/reporting date will be calculated as

$$\text{Day \#} = (\text{visit/reporting date} - \text{Day 1 date} + 1).$$

If the visit/reporting date is before Day 1, then the study day at the visit/reporting date will be calculated as

$$\text{Day \#} = (\text{visit/reporting date} - \text{Day 1 date}).$$

A study day of -1 indicates 1 day before Day 1.

4.1.3. Baseline Value

Baseline is the last nonmissing measurement obtained before or on the day of first application of ruxolitinib cream or vehicle cream for double-blind period.

For randomized participants not treated with any study drug, baseline is defined as the last nonmissing assessment before or on the day of randomization for all parameters.

For participants who continue in the treatment extension period, baseline is defined as follows:

- For efficacy evaluation, baseline is the last nonmissing measurement obtained before or on the day of first application of study treatment in double-blind period;
- For safety evaluation, for participants who cross over from vehicle group to ruxolitinib cream, the baseline is the last nonmissing measurement obtained before or on the day of first application of ruxolitinib cream in the extension period; for participants who applies ruxolitinib cream in both periods, baseline is the last nonmissing measurement obtained before or on the day of first application of study treatment in double-blind period.

When scheduled assessments and unscheduled assessments occur on the same day and time of the assessment or time of first application is not available, use the following convention to determine baseline:

- If both a scheduled and an unscheduled visit are available on the day of the first application and the time is missing, use the scheduled assessment as baseline.
- If all scheduled assessments are missing on the day of the first application and an unscheduled assessment is available, use the unscheduled assessment as baseline.

4.1.4. Handling of Missing and Incomplete Data

For response endpoints, including F-VASI75, F-VASI50, F-VASI90, T-VASI50, and VNS 4 or 5 as listed in the primary and key secondary endpoints, all participants who are missing postbaseline values, will be handled using MI under the missing-at-random assumption.

For continuous endpoints, any participant who is missing postbaseline values may have missing data handled using MMRM or MI under the missing-at-random assumption. MMRM model implicitly adjusts for missing data through a variance-covariance structure.

For other endpoints, missing observations will be handled as detailed in the specific sections addressing each analysis.

4.2. Variable Definitions

4.2.1. Body Mass Index

Body mass index (BMI) will be calculated as follows:

$$\text{BMI (kg/m}^2\text{)} = [\text{weight (kg)}] / [\text{height (m)}]^2.$$

4.2.2. Prior and Concomitant Medication

Prior medication is defined as any nonstudy medication started before the first application of study treatment.

Concomitant medication is defined as any nonstudy medication that is started accordingly:

- Before the date of first application of study treatment and is ongoing throughout the study or ends on/after the date of first application of study treatment.
- On/after the date of first application of study treatment and is ongoing or ends during the course of study treatment.

A prior medication could also be classified as "both prior and concomitant medication" if the end date is on or after the first application of study treatment. In the listing, it will be indicated whether a medication is prior-only, concomitant-only, or both prior and concomitant.

For the purposes of analysis, all medications will be considered concomitant medications unless the medications can unequivocally be defined as not concomitant.

5. STATISTICAL METHODOLOGY

5.1. General Methodology

Unless otherwise noted, SAS® software (SAS Institute Inc, Cary, NC; Version 9.1 or later) will be used for the generation of all tables, graphs, and statistical analyses. Descriptive summaries for continuous variables will include, but not be limited to, the number of observations, mean, standard deviation, median, minimum, maximum, 1st quartile, 3rd quartile, and 95% CI. Descriptive summaries for categorical variables will include the number and percentage of participants in each category.

5.2. Treatment Groups

This is a randomized, double-blind, vehicle-controlled study followed by a treatment extension period. Data will be summarized based on treatment regimen that was assigned (FAS) or that the participant actually applied (safety).

During the double-blind (DB) period, the treatment groups will be ruxolitinib cream 1.5% BID and vehicle cream.

During the treatment extension period, the treatment groups will be ruxolitinib cream 1.5% BID and vehicle to ruxolitinib cream 1.5% BID.

5.3. Analysis Populations

5.3.1. Full Analysis Set

All participants who are randomized and have baseline and any postbaseline assessments constitute the FAS. Treatment groups for this population will be defined according to the treatment assignment at the time of randomization regardless of the actual study treatment the participant might apply during his/her participation in the study. Those participants who have only study baseline, but not any postbaseline assessment are not included in the FAS.

The FAS will be used for the summary of analyses of demographics, baseline characteristics, participant disposition, and all efficacy data.

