10.2. Populations for Analysis

The populations for analysis are presented in [Table 15](#).

Table 15: Populations for Analysis

Population	Description
ITT	The ITT population includes all randomized participants. Treatment groups for this population will be defined according to the treatment assignment at randomization.
PP	The PP population includes randomized participants who are considered to be sufficiently compliant with the Protocol.
Safety	The safety population includes all participants who applied at least 1 dose of study drug. Treatment groups for this population will be determined according to the actual treatment the participant received on Day 1.
PK/ pharmacodynamic evaluable	The PK/pharmacodynamic evaluable population includes participants who applied at least 1 dose of ruxolitinib cream and provided at least 1 postdose blood sample for PK. The study pharmacokineticist will review data listings of participant administration and sample records to identify participants to be excluded from the analysis.

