10.3.1. Efficacy Analyses

10.3.1.1. Primary Analysis

The primary analysis will be based on the intent-to-treat population. The primary alternative hypothesis (superiority of ruxolitinib cream 1.5% BID compared with vehicle) will be tested using exact logistic regression ([Mehta and Patel 1995](#)). This model will include the treatment group (1.5% BID and vehicle) and stratification factors. The p-value for between-treatment

group testing will be compared with 0.05. Odds ratio and corresponding 95% confidence interval will be provided for comparing ruxolitinib cream and vehicle group at Week 24.

All nonresponders in the double-blind treatment period, as well as all participants who discontinue study treatment at any time before the timepoint of interest, or discontinue from the study for any reason, will be defined as nonresponders for the nonresponder imputation analysis.

Analysis will also be performed in the PP population for the primary endpoint. The following deviations are considered major:

- Missing primary endpoints on F-VASI;
- Compliance less than 60% based on the application numbers.

Participants with 1 or more such deviations will be excluded from the PP population. In addition, Protocol deviations related to inclusion/exclusion criteria, discontinuation criteria, and use of excluded concomitant medications will be evaluated and decided whether they should be excluded. Any exclusion from the PP population will be decided prior to breaking the blind.

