7.3.1. Primary Efficacy Analyses

The primary analysis will be based on the FAS population. The primary alternative hypothesis (superiority of ruxolitinib 1.5% BID compared with vehicle) will be tested using exact logistic regression (Mehta and Patel 1995). This model will include the treatment group (1.5% BID and vehicle) and stratification factors (skin type and region). The unadjusted p-values between each treatment group versus vehicle will be compared with the procedure defined in Section 3.2.

Odds ratio in response rates (ruxolitinib cream vs vehicle) at Week 24 will also be computed. All participants who are missing the F-VASI assessment at a given visit in the DB period will be handled using MI under the missing-at-random assumption. Rescue therapy is not allowed in the studies. Any participant who received rescue therapy will be considered as a protocol violation and will be imputed as a nonresponder. The numerical values for F-VASI will not be included in the MI model or other sensitivity analyses.

For MI, a fully conditional specification method (van Buuren 2007) that assumes the existence of a joint distribution for all variables will be used to impute F-VASI score. A regression model including treatment group, stratification factors, and baseline and postbaseline F-VASI scores up to Week 24 will be specified for the fully conditional specification method. The randomization seed will set to be 18424306 for Study INCB 18424-306 and 18424307 for Study INCB 18424-307. The imputation will be repeated 10 times to generate corresponding complete datasets, in order to reflect the uncertainty around the true value. After the missing values have been imputed, the binary variable F-VASI75 response will be derived. The exact logistic regression will be applied to each imputed dataset, and then the results will be combined for the inference.

The following is example SAS code for MI:

```
proc mi data=mi_wide seed=18424306 n impute=10 out=impute_fvasi;
  class trt01p strat1 strat2;
  var trt01p strat1 strat2 avalBASELINE avalWEEK4 avalWEEK8
  avalWEEK12 avalWEEK18 avalWEEK24;
  fcs;
run;
```

The following is example SAS code for exact logistic regression:

```
proc logistic data=fvasi75_mi exactonly;
  class trt01p (ref='VEHICLE CREAM') strat1 strat2/param=ref;
  model resp (event='Y') = trt01p strat1 strat2/covb;
  exact trt01p/estimate=both;
  by _Imputation_;
run;
```

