10.1. Changes to Protocol-Defined Analyses

- The FAS will be used to replace ITT in evaluation of the efficacy during DB period. The participants with only baseline but not any postbaseline assessments are excluded from the FAS. Those participants are not considered to be able to contribute to the efficacy analysis because of missing data in postbaseline visits.
- Multiple imputation will be used to replace the NRI to handle missing values in the analysis for primary and key secondary endpoints. Multiple imputation is able to provide unbiased estimates of the parameters under MAR.
- DLQI/CDLQI have been moved from exploratory endpoints to secondary endpoints.

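### The SAP drops randomised participants with no post-baseline assessment from every efficacy analysis, so even the nonresponder and worst-case tipping-point analyses do not cover everyone randomised

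*SAP*

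**What the plan says.** Protocol 10.2 (Amendment 3-US-CA, the version on which the SAP is based) defines the intent-to-treat set: "The ITT population includes all randomized participants". Protocol 10.3.1.1 then states: "The primary analysis will be based on the intent-to-treat population". Protocol 10.3.1.2 uses the same set for the key secondary endpoints.

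SAP 5.3.1 requires a baseline and some post-baseline assessment for entry to the FAS, and adds: "Those participants who have only study baseline, but not any postbaseline assessment are not included in the FAS". It gives that set a wide scope: "The FAS will be used for the summary of analyses of demographics, baseline characteristics, participant disposition, and all efficacy data". SAP 7.3.1, 7.4, 7.5.1 and 7.6.1 name the FAS for the primary, key secondary, other secondary and exploratory analyses. The per-protocol set (5.3.2) is a subset of the FAS. Appendix A lists the tipping-point table (2.1.1.9) on the FAS. Sections 7.3.3.1 (NRI) and 7.3.3.2 (LOCF) name no other set, so the rule in 5.3.1 applies to them.

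SAP 10.1 declares the change and gives its reason: "Those participants are not considered to be able to contribute to the efficacy analysis because of missing data in postbaseline visits".

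**The concern.** Whether a participant enters the FAS depends on something that happens after randomisation, namely coming back for at least one assessment. Any difference between arms in who never returns is then removed from view.

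The larger problem is where the removal takes effect. NRI and the tipping-point analysis exist to show whether missing data could overturn the primary result. Participants with no post-baseline data have the most missing data of anyone, and they are taken out before either analysis starts. What the SAP calls the most conservative case is therefore not the worst case for the trial as randomised. A reader could be told that the result survives the extreme scenario when it would not survive it on the randomised set.

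**Working it through.** **1. Does the stated reason hold?** Set it beside the methods in the same SAP.

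- Multiple imputation (7.3.1) uses "A regression model including treatment group, stratification factors, and baseline and postbaseline F-VASI scores up to Week 24". Arm, strata and baseline are known for a baseline-only participant, so the model can impute the rest.
- SAP 4.1.4 says, for the response endpoints, that "all participants who are missing postbaseline values, will be handled using MI under the missing-at-random assumption". Read literally, that includes baseline-only participants.
- NRI (7.3.3.1) counts anyone missing post-baseline values as a nonresponder. It needs no post-baseline value.
- The tipping-point grid (7.3.3.3) assigns outcomes to missing participants by design.
- LOCF (7.3.3.2) does need a post-baseline value. The reason holds for this method only.

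SAP 4.1.1 and 4.1.3 also define Day 1 and baseline for participants randomised but never treated. If such a participant has baseline only, he or she is outside both the safety population and the FAS.

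**2. Inputs.** About 300 participants randomised 2:1, taken as 200 and 100; F-VASI75 at Week 24 of 20% vs 5%; Fisher's exact test, two-sided 0.05 (SAP 3.3). Fisher's test is also the tipping-point test in SAP 7.3.3.3. The number with baseline only is not given, so it is varied as an assumption.

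**3. The plan's own figure.** Stated power for the primary endpoint is 95%. Exact enumeration at 200 vs 100 gives 96.6% (95.8% with 0.025 in each tail), so the figure reproduces within 2 points. Dropping 1%, 2%, 3% or 5% of each arm gives 96.4%, 96.2%, 96.0% or 95.5%. Power is not the issue.

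**4. Nonresponder analysis.** FAS response rates are held at plan, with responder counts rounded.

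- Balanced loss of 5% per arm: FAS 38/190 vs 5/95 (20.0% − 5.3% = 14.7 points, p=0.0007). All randomised, with the excluded counted as nonresponders: 38/200 vs 5/100 (19.0% − 5.0% = 14.0 points, p=0.0008). The effect is small.
- Loss of a fraction e in the active arm only: the FAS overstates the difference by 0.20 − 0.20 × (1 − e) = 0.20e. That is 0.4, 1.0 and 2.0 points at e = 2%, 5% and 10%.

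**5. Worst case with nothing missing inside the FAS.** Excluded active participants count as nonresponders and excluded vehicle participants as responders.

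| Baseline-only per arm | FAS, p | All randomised | p |
|---|---|---|---|
| 3% | 0.0005 | 39/200 vs 8/100 | 0.011 |
| 5% | 0.0007 | 38/200 vs 10/100 | 0.047 |
| 6% | 0.0007 | 38/200 vs 11/100 | 0.097 |

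**6. The planned tipping-point analysis, with some Week 24 values also missing inside the FAS.** For 4% missing in the FAS and 2% baseline-only, 188 active and 94 vehicle participants are observed. Responders are 0.20 × 188 = 37.6, rounded to 38, and 0.05 × 94 = 4.7, rounded to 5. The SAP's case adds 4 vehicle responders, giving 38/196 vs 9/98. All randomised adds 2 more, giving 38/200 vs 11/100.

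| Missing in FAS + baseline-only, per arm | SAP most conservative case, p | All-randomised worst case, p |
|---|---|---|
| 2% + 2% | 0.006 | 0.028 |
| 3% + 3% | 0.016 | 0.097 |
| 4% + 2% | 0.028 | 0.097 |
| 4% + 3% | 0.040 | 0.186 |
| 5% + 1% | 0.046 | 0.097 |
| 6% + 0% | 0.097 | 0.097 |

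In a grid of 0–6% missing in the FAS by 0–3% baseline-only (7 × 4 = 28 cells), the reading changes in four: 3%+3%, 4%+2%, 4%+3% and 5%+1%.

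**The case against.** The change is declared in SAP 10.1, and Protocol 10.3 leaves missing-data procedures to the SAP. The excluded group should be small. Any post-baseline assessment admits a participant to the FAS, and someone who stops early should still have an end-of-treatment visit that includes F-VASI. Protocol 2.4.2.2.3 calls Phase 2 discontinuation low, with adverse event rates similar between active and vehicle. That points to few and roughly balanced losses.

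The tipping cells are few and sensitive. Three of the four share one table, 38/200 vs 11/100. If 4.7 vehicle responders are rounded down to 4, that table becomes 38/200 vs 10/100, p=0.047, and those three no longer tip. At the Phase 2 active rate of 30.3%, with vehicle kept at 5%, no cell tips; the largest all-randomised p is 0.009. The worst case also assumes that every vehicle participant who never returned reached F-VASI75, when 5% is planned and 0% was seen in Phase 2.

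Most of this stands as a limit on size. It does not restore the excluded participants. Declaring a change does not justify it when the reason fails for three of the four methods. Rounding down moves the affected cells to 4%+3%, 5%+2% and 5%+3% rather than removing them. Extreme assumptions are what the end of a tipping-point grid is for, and that end should be the true one. SAP 4.1.4 could be read as covering only FAS members who missed some visits, so it is supporting evidence and not proof of a contradiction.

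**Conclusion.** The concern holds. The SAP contains no efficacy analysis on all randomised participants, contrary to Protocol 10.2 and 10.3.1.1, and the reason given for the change is sound only for LOCF.

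The primary imputed estimate would move little under missing at random, because baseline-only participants would be imputed from arm, strata and baseline alone. Power falls by about one point at 5% exclusion (96.6% to 95.5%). Balanced losses barely change NRI. The practical loss is that the stated worst case is too mild. At planned rates, 1% to 3% baseline-only per arm can separate a result that holds from one that tips, when 3% to 5% are also missing inside the FAS. This rests on assumed missing-data rates, on planned response rates that are lower in the active arm than Phase 2 showed, and on rounded counts. It should be fixed, although it is unlikely to decide the trial.

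**What to change.** - Use all randomised participants for the primary and key secondary analyses, as the protocol says, with baseline-only participants imputed in the existing model. At the least, use them for NRI and the tipping-point grid.
- In NRI, count baseline-only participants as nonresponders. In the tipping-point grid, count them among the missing.
- While editing NRI, restore the protocol's rule, which also covers "all participants who discontinue study treatment at any time before the timepoint of interest". This is a separate gap in SAP 7.3.3.1, and the present point does not depend on it.
- Keep the FAS as supportive. Leave LOCF on the FAS unless a rule for baseline-only participants is added.
- Report the number excluded from the FAS by arm, with reasons, and show disposition on all randomised. Table 1.1.1 covers all participants, but the disposition table (1.1.2.1) is on the safety population and FAS only.

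The cost is SAP wording and table footnotes; no new data are needed. NRI response rates may be slightly less favourable. If few participants are excluded, the results will hardly change.
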